Under the Privacy Act of 1974 (5 U.S.C. Section 552(e)), employees of federal agencies are responsible for protecting data collected on identifiable persons or organizations where the supplier of information has not given the agency consent to make that data public. This responsibility for protection includes unauthorized visual observation of confidential material, accidental loss, and theft of data. Accordingly, confidential records will be kept out of sight of unauthorized persons, stored in locked cabinets or locked in rooms when not being used, copied only when absolutely necessary, and stored in sealed containers when transferred to archives. To assure privacy and confidentiality, each participant will be assigned a unique identification number that will be placed on the questionnaire, consent forms, and any other information collected from the participant. Computerized data analysis files will contain identification numbers only.

To access the web-based survey, participants will receive a personal identification number (PIN) to be used for authentication to ensure that only the study population can participate in the survey and that the survey is not completed more than once by the same

participant. Data collected over the internet will be transmitted in an encrypted format to ensure that any data intercepted during transmission cannot be decoded; data will also be stored in an encrypted format on password-controlled servers to protect personally identifiable information.

The study is performed for the purpose of developing or contributing to generalizable knowledge. There are no physical risks involved. No social, economic, legal, or other risks are anticipated. Questions about cancers and other diseases may be sensitive to some persons, but are not more than minimal risk. The questionnaire will be reviewed and approved by the CDC/ATSDR IRB prior to being administered to participants.

All respondents will be informed that providing the requested information is entirely voluntary and informed consent will be obtained. Those participants who complete the survey on-line will be informed that they can print out a copy of the consent form for their records. Additionally, they will be told that by clicking the “I agree” button on the computer screen, they are agreeing to take part in the survey. Reports of statistics derived from confidential data will be presented in such a way as to avoid inadvertent disclosure about specific study subjects. Final reports from this study will not contain medical information or findings in association with any individual subject. All records will continue to be maintained in compliance with the Privacy Act of 1974.

Requested Waivers

We are requesting a waiver of documentation of informed consent according to 45 CFR 46.117(c)(2) because the research represents no more than minimal risk of harm to subjects. The waiver is only requested for participants who complete the web-based

survey. The web-based survey takes approximately 45 minutes and participants must click the “I agree” button before beginning the survey. We are also requesting a waiver of the prisoner regulations since the research does not fit into the research categories specified in 45 CFR46.306. This waiver allows inclusion of prisoners in epidemiological research if (1) the epidemiologic study's sole purposes are “to describe the prevalence or incidence of a disease by identifying all cases, or to study potential risk factor associations for a disease”; (2) the study poses no more than a minimal risk and no more than an inconvenience to the prisoner; and (3) “prisoners are not a particular focus of the research.” This study meets all of these criteria: 1) the study's purpose is to describe the prevalence and risk factors for health problems related to exposure to TCE contaminated water at the Camp Lejeune military base, 2) the study poses no more than minimal risk and participation would be no more that an inconvenience to the prisoner, and 3) the focus of the research is not prisoners, but people formerly stationed at or employed by the Camp Lejeune marine base.

Quality Control

All electronically entered information obtained from surveys will be reviewed for missing data and ambiguous responses. Internal consistency and validity programs will be used to identify and correct coding and data entry errors. The web-based survey will include prompts to alert participants if they incorrectly answer or skip questions; drop down boxes that present ranges of possible answers; and electronic skip patterns that automatically skip irrelevant questions.

Data Analysis

The civilian employees will be analyzed separately from the active duty personnel

and their dependents. This is because the primary exposure to drinking water contaminants for the civilian employees is not the residence, but the workplace location. If the exposure-response relationship for a specific condition in the analysis of civilian employees is observed to be similar to that observed in the analysis of active duty personnel and their dependents, then a combined analysis may be conducted.

In the analysis of active duty personnel and their dependents, there are no dependents from Camp Pendleton. It will be assumed that dependents and active duty personnel with similar residential drinking water exposures (including no exposure) will have similar risks for a condition. In subsequent analyses, effect modification of the exposure-response relationship for a specific condition by whether the respondent was a dependent or active duty personnel will be explored.

Person-time will accumulate from the date the person first resided or worked at Camp Lejeune (or Camp Pendleton) until date of death or the date that the health surveys are mailed. The monthly average levels of contaminants in the drinking water will be used to estimate exposure. The exposure intensity (average and maximum exposure level), exposure duration, and cumulative exposure measures will be calculated. In addition, these exposure measures will be categorized using a priori meaningful cutpoints and/or quantiles based on the exposure distribution of respondents from Camp Lejeune, and cutpoints from a smoothing procedure (e.g., splines or LOESS). The monthly Monte Carlo 95% interval range for each contaminant will be taken into account during the categorization of exposure variables.

The analyses will focus on reported diseases of interest that are confirmed by medical record, death certificate, or cancer registration. However, because medical

records are generally unavailable for miscarriages, a miscarriage will be considered “confirmed” if affirmative responses are provided to two survey questions: “Did you have a positive pregnancy test before the miscarriage occurred?” and “Was the miscarriage confirmed by a physician or other health provider?” These two questions have been found to improve the accuracy of self-reports of miscarriages (Axelsson 1990).

Poisson regression methods will be used to evaluate exposure-disease relationships, with exposure measures and potential confounding factors included in the models as independent variables. Logistic regression may be used to check the Poisson regression results. Survival analysis methods with age as the time variable may also be used to evaluate relationships between disease and continuous exposure (and confounder) variables. Exposure will be lagged to account for an appropriate latency period for each condition. For most cancers, the initial analyses will lag exposure by 10 years (i.e., a 10-year latency period). Additional analyses will explore other latency periods for each condition. Selection of risk factors for inclusion in the models as confounders will be based on a “10% change in the estimate” rule (Maldonado and Greenland 1993). Models will also be constructed that include well-known risk factors for the disease under evaluation from information obtained in the survey. Ninety percent confidence intervals will be calculated for parameter estimates.

The first confirmed diagnosis of a generalized skin disorder will be used in the analysis. For miscarriage, two approaches will be used. First, we will evaluate only the first pregnancy that occurs at the base. Second, we will include all pregnancies that occur

in the follow-up period and employ the generalized estimating equation (GEE) approach to account for non-independent outcomes arising from multiple pregnancies for the same woman. Induced abortions and ectopic pregnancies will be excluded from the analyses of miscarriage. For the GEE analyses, the logit link will be employed and the correlation structure will assume equal correlation between birth outcomes for the same woman.

All comparisons will be “internal comparisons” where the Camp Pendleton cohorts will be the unexposed group. If those at Camp Lejeune whose residences were not served by contaminated water have a similar risk for a specific disease as the Camp Pendleton cohorts, then they will be included along with the Camp Pendleton cohorts in the unexposed group. If their risks are observed to be different, then an indicator variable will be included in the analyses that distinguishes the unexposed at Camp Lejeune from the unexposed at Camp Pendleton.

Since drinking water in the field was provided in tanks and “buffaloes” that could have come from anywhere on base, but most likely came from Hadnot Point, it was deemed possible that all active duty personnel were exposed to contaminated drinking water at Camp Lejeune during their field training. This is the primary reason why unexposed comparison groups from Camp Pendleton are necessary. In the subsequent analyses, it will be assumed that all active duty Marines had the potential for drinking water exposures in the field. A variable for field drinking water exposure (based on the contamination levels at Hadnot Point during the period when the individual was stationed at the base) will be added to the Poisson (or Cox) regression models.

Sensitivity Analyses of Selection and Information Biases

For selection bias (or non-response bias) to be present, participation rates must

vary jointly by exposure and disease status. Since disease information is not available for non-respondents, the likelihood and magnitude of selection bias cannot be addressed directly. One indirect approach to assess the likelihood and magnitude of selection bias is to compare exposure-disease association measures (i.e., rate ratios and exposure-response trends) for specific, confirmed cancers in the morbidity study with the preliminary results for those cancers in the mortality study of former marines and civilians potentially exposed at Camp Lejeune. Cancers which are not known or suspected of being associated with the drinking water exposures (e.g., colon/rectal, prostate, stomach, and melanoma) will be evaluated. If for several cancers, substantial discrepancies that are not biologically plausible are found between the results of the mortality study and the morbidity study (e.g., for a specific cancer, the mortality study has an SMR close to 100 but the morbidity study has an RR greater than 2.0), then this may be evidence of bias in the morbidity study. However, in addition to selection bias, disease information bias, in particular, under-reporting of diseases by the Camp Pendleton comparison population, could produce discrepancies between the morbidity study and mortality study results. Although substantial under-reporting is not expected for cancers, under-reporting in the Camp Pendleton sample will be evaluated by comparing the incidence of reported, confirmed specific cancers in the Camp Pendleton sample with incidence rates from the Surveillance, Epidemiology and End Results (SEER) program and from a cancer incidence study of veterans (Harris et al. 1989). Underreporting by the Camp Lejeune respondents will be assessed in the same manner.

A second approach to evaluate the impact of potential selection bias will be to conduct sensitivity analyses to determine what level of bias would have to be present to

explain differences between groups. For diseases having elevated rate ratios (e.g., RRs > 2.0), we will determine the amount of selection bias that would be necessary to produce the observed RRs if the true RR =1 using several different scenarios with the following assumptions:

- Responders have a higher disease rate than non-responders regardless of exposure status (Tao et al. 2007)
- Exposed responders have a higher disease rate than exposed non-responders, Camp Pendleton responders, or Camp Pendleton non-responders

Confirming diagnoses will minimize information bias due to over-reporting of conditions. However, confirmation may not be possible for all reported conditions of interest. To assess the extent of information bias due to inability to confirm diagnoses, the percentages of (1) medical record confirmation, (2) medical record disconfirmation, and (3) no available medical record, will be compared between the unexposed and exposed groups for the diseases of interest. In addition, sensitivity analyses will be conducted that include diagnoses for which no confirmation was possible as well as confirmed diagnoses to determine if inclusion of the non-confirmed diagnoses modifies exposure-response relationships. To minimize bias due to underreporting of conditions, (e.g., a problem that might occur among the Camp Pendleton cohorts), the pre-notice letter and the letter accompanying the health survey questionnaire will avoid mentioning the hypotheses under investigation and will not indicate who is considered exposed or unexposed.

Interpretation and Dissemination of Results

ATSDR will publish a final report of the study which will be distributed to the general public by posting it on the ATSDR Camp Lejeune website. Additionally, a presentation will be made to the USMC, the (DON, and the CAP. ATSDR will also publish the results in a peer-reviewed scientific journal. Only aggregate data presented in tables and graphs will be published and presented.

Study participants will be mailed a summary of the final report. Because the study population is dispersed over a wide geographic area, ATSDR will develop a web broadcast that discusses the results of the study. Study participants will be mailed a letter that provides the internet address for the web broadcast and also tells them how to receive a copy of the web broadcast on CD-ROM if they do not have internet access. ATSDR will update our Camp Lejeune website to include the full final study report as well as a link to the web broadcast. If study participants or other interested parties have questions about the study, they can email or call ATSDR. ATSDR will set-up a response line staffed with operators who are dedicated to answering questions about the study. The operators will also respond to emails. Telephone operators will receive extensive training on how to respond to calls and emails including response line procedures, frequently asked questions, and when to triage calls/emails to study investigators.

In order to keep respondents informed of the latest developments at Camp Lejeune concerning the drinking water contamination and health issues, ATSDR will share with the USMC updated current addresses obtained as part of the health survey mailings; the USMC already has the names and contact information of the study participants and no other information will be provided to the USMC. The USMC is required by Congress to notify former residents and employees who were at Camp

Lejeune during the period of water contamination about the results of studies and other pertinent public health information. The USMC will follow appropriate measures to maintain the confidentiality of the contact information.

Communicating results of environmental epidemiology studies to the general public is often complicated and challenging. Scientific concepts may be difficult for the general public to understand and there may be trust issues between the community and the federal government. To overcome these challenges, ATSDR will engage its public communications staff to assist the Camp Lejeune researchers in communicating the results of the studies. Study participants will be informed of how ATSDR measured associations and the criteria used to interpret the meanings of the associations. Specifically, ATSDR will calculate incidence rate ratios and 90% confidence intervals for each exposure-disease relationship. Incidence rate ratios (RRs) compare the disease rates among various levels of exposed to the disease rate among the unexposed adjusting for confounders. Exposure-response relationships are examined by determining whether the RRs increase with increasing exposure level. If the disease rates are the same in the exposed and unexposed groups, then the RR is equal to or close to 1.0. A RR close to or equal to 1.0 indicates that there is a lack of association between the exposure and the disease in the data. If the exposed group has a higher disease rate than the unexposed (i.e., RR is greater than 1) or if there is a trend of increasing disease rate with increasing exposure, then there is an association between exposure and disease in the data. A confidence interval provides information on the precision of the RR. The width of the confidence interval reflects the amount of variability in the RR. The wider the confidence interval, the less precise and more uncertain is the estimate of the RR. The

interpretation of each exposure-disease relationship will take into account the following:

- the strength of the association (the magnitude of the incidence rate ratio or RR),
- dose-response effect (as concentration of TCE/PCE/benzene and/or the amount of water consumed increases, so does the risk of having a cancer or other disease),
- temporality (with consideration of an appropriate latency period),
- the consistency of findings, both within the study and when compared to other epidemiologic studies, and
- biological plausibility.

In addition, the interpretation of each exposure-disease relationship will take into account the results of the sensitivity analyses of potential biases (e.g., non-response bias, disease reporting biases, and exposure misclassification). “Sub-group” analyses (e.g., examining different exposure metrics and exposure lag periods, evaluating major sub-groupings of a disease such as leukemia, and estimation of effect modification between exposure and another factor) will be conducted in order to provide supplemental information on the exposure-disease relationship. The relationship between each exposure of interest (i.e., residential drinking water exposure to a particular VOC) and each disease of interest listed in the procedures will be evaluated as a separate, *a priori*, hypothesis. Each of these hypotheses has scientific interest in its own right and will be qualitatively different from each of the other hypotheses on characteristics such as the target organ, the biological mechanism of effect, the dose-response relationship, the effect of latency, the effect of possible confounders, and the strength of the prior evidence in the scientific

literature for a causal association.

ATSDR will ensure that the affected community is given information at an appropriate educational level. ATSDR will also emphasize that the ATSDR morbidity study cannot by itself establish a causal link between population exposures at Camp Lejeune and specific diseases in an individual. The affected community will be informed that the purpose of ATSDR's research is to contribute to our understanding of the human health effects related to exposures such as VOCs in drinking water. The study results will add information to the overall weight-of-evidence about human health outcomes and exposures to TCE, PCE, benzene and other solvents found in the contaminated drinking water at Camp Lejeune.

ATSDR will also set appropriate expectation for the morbidity study. ATSDR cannot guarantee that the morbidity study will find positive associations or that it will provide answers to all of the community's questions. ATSDR will acknowledge that the observation of an association doesn't mean that there is a cause and effect relationship. ATSDR will also acknowledge that the absence of an observed association does not exclude the possibility of an association existing.

The limitations of the morbidity study will be appropriately communicated. The limitations are due to uncertainties related to exposure assessment and potential study biases (i.e., non-response bias, information bias, and inadequate control of confounders).

DISCUSSION

This is one of only a few studies to examine the associations between cancers and specific other diseases and exposures to VOCs in drinking water. The proposed study has limitations, primarily due to uncertainties related to exposure assessment and the potential

for response and non-response biases. However, steps will be taken to reduce these biases when possible and to assess the impact of potential biases on the estimates of effect (i.e., RRs) and exposure-response relationships.

A differential nonresponse bias would occur if the response rate is related to both disease status and exposure status. For example, if those exposed with health problems have a higher response rate than either those exposed without health problems or those unexposed with health problems, then a bias away from the null would result. To minimize the possibility of differential nonresponse, ATSDR will request that the highest ranking officer of the USMC sign the introductory letter to encourage participation among former active duty Marines, including those without health problems. However, although important to the success of this study, achieving a high participation rate will not necessarily eliminate non-response (or selection) biases. Therefore, sensitivity analyses will be conducted to assess the possible impact of non-response biases.

Confirming disease reports will be crucial to the success of this study. ATSDR will work with the DOD and VA cancer registries as well as the cancer registries in all 50 states and the District of Columbia to set up a mechanism for confirming self-reported cancers. For non-cancer outcomes, the survey will obtain information that should facilitate the confirmation of these outcomes. ATSDR will also seek the assistance of the VA and the Naval Health Research Center to confirm these outcomes.

Ascertainment bias may be a problem if some participants do not accurately report diseases that they may have had (Bergmann et al. 1008; Desai et al. 2001; Freedman et al. 2006; Parikh-Patel et al. 2003; Schrijvers et al. 1994). In particular, there is a possibility that cancers and other conditions may be underreported. If underreporting

is associated with exposure status, a differential bias would occur. To assess the impact of possible underreporting bias in the reporting of cancers, the rates of confirmed cancers in the exposed and unexposed groups will be compared to national rates. Anticipating that both response biases and underreporting of cancers may be problems, ATSDR is considering conducting a cancer incidence data linkage study that would send the names and other identifying information of everyone in the study population (including those who do not respond to the survey) to the 50 state cancer registries and to the DOD and VA cancer registries. If the state and federal cancer registries agree to participate in this cancer incidence data linkage study, then ATSDR will develop a protocol and submit it for IRB approval.

Several sources of information will be used in the exposure assessment. The historical reconstruction of the Tarawa Terrace and Hadnot Point drinking water systems at Camp Lejeune, utilizing state-of-the-art contaminant fate, transport and distribution models, will provide the maximum likelihood monthly estimate of the level of each contaminant in each system as well as a 95% interval for each estimate based on Monte Carlo simulations. The exposure metrics used in this study will be based on these contaminant estimates. Information on the base residences and workplace locations will be obtained from the survey as well as from family housing records. Additional information on the locations where units were barracked and on workplace locations will be provided by current and former base staff and knowledgeable former Marines. No other information relevant to drinking water exposures at Camp Lejeune is available. The available information on exposures is sufficient to conduct a valid, scientifically sound study. However, exposure misclassification bias remains a possibility in this

study. To reduce bias due to errors in the recall of residential/worksite address on base, the survey information will be supplemented by information from base family housing records and personnel records (e.g., unit identification codes and occupation codes). In addition, sensitivity analyses will be conducted to assess the impact of possible exposure misclassification bias on the estimates of RR as well as exposure-response relationships.

While there is no direct public health benefit to those participants potentially harmed by the contaminated drinking water at Camp Lejeune, the information gained during the study will help advance research on this topic and may help future populations. Only two populations have been studied with regard to the risk of adult cancers among those exposed to VOCs in drinking water. This study is unique because it will use monthly contaminant level estimates to define drinking water exposures.

USMC REGISTRANTS

The National Defense Authorization Act for Fiscal Year 2008 mandated that everyone who registered with the USMC receive a health survey. To comply with this law, ATSDR will mail health surveys to all registrants. However, registrants will not be included in the morbidity study unless they are also a member of the study population defined above. The surveys completed by registrants who are not members of the study population will be analyzed separately, primarily in a descriptive manner (i.e., demographics and the percent reporting each disease). Registrants will have separate invitation letters (Appendix 5) and informed consents (Appendix 6) and the Dillman Total Design Method will not be employed. Confirmation of reported diseases will not be sought for registrants who are not members of the study population.

REFERENCES

- Agency for Toxic Substances and Disease Registry. (ATSDR) 1998. Volatile Organic Compounds in Drinking Water and Adverse Pregnancy Outcomes: U.S. Marine Corps Camp Lejeune. Onslow County, North Carolina. Atlanta: US Department of Health and Human Services.
- Axelsson G. Use of questionnaires in a study of spontaneous abortion in a general population. *J Epidemiol Community Health* 1990; 44:202-204.

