The exposure assessment will be based on groundwater contaminants fate and transport and water distribution system models for the Hadnot Point, Holcomb Boulevard, and Tarawa Terrace drinking water systems. These models will provide historical monthly average levels (and Monte Carlo 95% interval ranges) of contaminants in the drinking water distribution systems serving family housing and bachelor quarters on base from the period when these drinking water systems came on line until contaminated wells in the Hadnot Point and Tarawa Terrace systems were shut down.

Enrollment of Study Participants

One to two weeks before the survey is mailed (Appendix 1), a pre-notice letter will be mailed (Appendix 2), signed by the highest ranking officer of the USMC, informing potential respondents that they will shortly receive a questionnaire in the mail and encouraging their participation. If a study participant is known to be deceased, the survey will be mailed to the next of kin if the name and address are available. To determine those in the study population who have died, name, date of birth, and SSN will be matched with the Department of Veterans Affairs Beneficiary Identification Records Locator System (VA BIRLS), the Social Security Administration (SSA) Death Master File, the Medicare Vital Status File, and the National Death Index (NDI), and the death

certificate from the health department in the state where the death occurred will be requested. Information provided by the USMC as part of its notification process will also be used to identify those who have died as well as next-of-kin. The information on the deceased person's health conditions and risk factors will be included in the morbidity study only if a completed health survey is received from the next-of-kin.

Data Collection

To determine the optimum length of the survey instrument that still answers the research questions of interest, the survey has been pilot tested on five volunteers. The findings of this pilot testing were that the average length of time to complete the survey was 45 minutes and that some of the skip patterns needed to be changed.

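### The only next-of-kin source the protocol names is tied to Camp Lejeune, so fatal cases may be captured more completely there than at Camp Pendleton, the reference group

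*Protocol*

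**What the plan says.** Under Enrollment of Study Participants, the protocol sets out three steps for members who have died.

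- **Finding deaths.** To determine those "in the study population who have died, name, date of birth, and SSN will be matched with" four files: VA BIRLS, the SSA Death Master File, the Medicare Vital Status File and the NDI. This step covers the whole study population, and death certificates are requested.
- **Reaching a proxy.** For a known decedent, "the survey will be mailed to the next of kin if the name and address are available". Information "provided by the USMC as part of its notification process will also be used to identify those who have died as well as next-of-kin".
- **Inclusion.** The decedent's data "will be included in the morbidity study only if a completed health survey is received from the next-of-kin".

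Interpretation and Dissemination of Results describes the notification: "The USMC is required by Congress to notify former residents and employees who were at Camp" Lejeune. The same paragraph says "the USMC already has the names and contact information of the study participants and no other information will be provided to the USMC".

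Data Analysis makes all comparisons internal, "where the Camp Pendleton cohorts will be the unexposed group". Lejeune members whose residences had uncontaminated water join the reference group only if their risk for the disease is similar to Pendleton's. Otherwise an indicator variable separates the two unexposed groups.

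**The concern.** For a living member, inclusion depends on that person's own response. For a decedent, it depends on whether a relative can be found and then replies. The four death files are described as a means of finding deaths, not relatives. The locator firm, under Morbidity Study Population, is described as finding current addresses and names for the study population, with no mention of relatives. That leaves the USMC notification process as the only named next-of-kin source, and its stated addressees are people from one of the two bases being compared.

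If next-of-kin are located more often at Lejeune, a larger share of Lejeune's fatal cases is counted. The rate ratio against Pendleton then rises without any effect of the water, and it rises most for diseases in which most cases have died by the mailing. The contrast matters to this design: the protocol gives possible field exposure of all active duty personnel at Lejeune as the main reason it needs a Pendleton comparison group.

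No planned check isolates decedents. The participation strata under Non-response (Selection) Bias include base and exposure group but not vital status or proxy response. The participation rate has as its denominator only sampled people with a current address, so a decedent with no located next-of-kin may drop out of it unseen.

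**Working it through.** **Inputs from the protocol (Table 1 and its notes).** Participation is 65%, giving 160,550 Lejeune and 39,000 Pendleton respondents. Type 1 error is 0.10 two-sided and power is 90%.

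**The plan's own figure.** Table 1 serves here only as a yardstick for size. With 10% of Lejeune unexposed there are 39,000 + 16,055 = 55,055 unexposed and 160,550 − 16,055 = 144,495 exposed. At a baseline of 0.08%, a two-proportion calculation gives a minimum detectable rate ratio of 1.59 without and 1.61 with a continuity correction, against 1.62 in the table. With the correction, all 40 cells agree within 0.02.

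**Inputs not in the protocol (assumptions).** The fatal share of cases f is set at 10%, 50% and 90%. Next-of-kin capture is 40% at Lejeune (r_L) and 40%, 30% or 20% at Pendleton (r_P). Living members participate at 65% at both bases. Person-time is treated as nearly unaffected.

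**Formula, at a true rate ratio of 1 with Pendleton as the only reference:**

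observed RR = [(1 − f) × 0.65 + f × r_L] / [(1 − f) × 0.65 + f × r_P]

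- f = 50%: the numerator is 0.325 + 0.200 = 0.525. Against 0.325 + 0.150 = 0.475 this gives 1.11; against 0.325 + 0.100 = 0.425 it gives 1.24.
- f = 90%: the numerator is 0.065 + 0.360 = 0.425. Against 0.065 + 0.270 = 0.335 this gives 1.27; against 0.065 + 0.180 = 0.245 it gives 1.73.

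| Fatal share | 40% v 40% | 40% v 30% | 40% v 20% |
|---|---|---|---|
| 10% | 1.00 | 1.02 | 1.03 |
| 50% | 1.00 | 1.11 | 1.24 |
| 90% | 1.00 | 1.27 | 1.73 |

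**If unexposed Lejeune members are pooled into the reference.** The denominator becomes a weighted average of the two bases. Pendleton's weight is 39,000 / 55,055 = 0.708 if 10% of Lejeune is pooled, and 39,000 / (39,000 + 48,165) = 0.447 if 30% is. For capture of 40% v 20%:

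- f = 50%: 0.525 / (0.708 × 0.425 + 0.292 × 0.525) = 1.16 with 10% pooled, and 1.09 with 30%.
- f = 90%: 0.425 / (0.708 × 0.245 + 0.292 × 0.425) = 1.43 with 10% pooled, and 1.23 with 30%.

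**Set against Table 1.** Its columns assume this pooling, so the pooled figures are the like-for-like ones. In the most extreme case shown, 1.43 exceeds the smallest detectable values in the 10% column (1.33 to 2.43), while 1.23 lies below every value in the 30% column (1.30 to 2.26). This compares size only, because the protocol gives no fatal share for any disease.

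**The case against.** The strongest reply is that the asymmetry is inferred. A reader might infer that the notification process covers only Lejeune, and so that fatal cases will be over-counted there. The documents do not support that certainty. The protocol never says the process is limited to Lejeune, and its remark about contact information for study participants is not restricted to one base. It gives no next-of-kin location or response rate for either base, and equal capture means no bias. This stands, and it is why the point is worded as a possibility. The remark does not settle the matter, though: members' contact details are not those of their relatives, and the sentence explains why updated addresses are shared.

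A reader might also infer that Pendleton families get no comparable prompt to respond. The mailing sequence (pre-notice letter, survey, reminder, second survey, telephone) makes no distinction by base, and the invitation and consent do not mention the contaminated water. Awareness may differ, but the study's own prompts do not.

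Third, the gap is by base, not by exposure. Unexposed Lejeune members share the same next-of-kin route, so exposure-response contrasts within Lejeune are untouched and pooling dilutes the bias. Both stand. However, pooling is conditional on similar risk, and a large capture gap makes that condition harder to meet. The indicator variable then leaves the contrast with Pendleton undiluted.

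Fourth, planned checks could partly reveal the problem: the comparison of unexposed Lejeune members with Pendleton, the comparison of each base with SEER and veteran rates, the mortality-study comparison, and the registry linkage under consideration. None separates lost decedents from other causes. The SEER comparison covers cancers only, the mortality comparison uses cancers not suspected of association, and the selection-bias scenarios are aimed at elevated rate ratios, with values above 2.0 as the example.

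**Conclusion.** The point holds as a possible base-level difference in capturing fatal cases. As written, the protocol makes a decedent's inclusion depend on reaching a next-of-kin, names one source for doing so, and ties that source to Lejeune. Identification of deaths is not the problem, since it is the same at both bases.

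The direction is upward for Lejeune-versus-Pendleton rate ratios if capture is better at Lejeune. The size cannot be known from the document. Under the stated assumptions it is negligible when few cases are fatal (1.02 to 1.03 at 10%), 1.11 to 1.24 when half are, and 1.27 to 1.73 when 90% are. It is smaller with pooling and nil with equal capture. These figures show what a gap of 10 or 20 percentage points would do; they do not predict that such a gap will occur.

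**What to change.** In Enrollment of Study Participants, state that next-of-kin will be traced at both bases with the same sources and effort, for example by extending the work of the locator firm already planned, and that the source of each next-of-kin contact will be recorded.

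Report by base the share of known decedents with a completed survey. Use as the denominator all decedents found by the planned death matching, whether or not an address was found.

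Repeat the Lejeune-versus-Pendleton analyses (a) without decedents whose next-of-kin came only from the USMC notification process, and (b) in living respondents only. Once tracing is equal, there is no need to remove the first group from the primary analysis; doing so would discard confirmed fatal cases.

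The cost is modest extra tracing, one source field and two further analyses, with fewer fatal cases and so less precision in those sensitivity analyses.
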